9.3.4 Sensitivity Analyses

9.3.4.1 Validation of the Cut Point for PROMISE Risk Score

The prognostic cut point used for the PROMISE risk score will be validated in light of the results of PRECISE. The calibration and discrimination of PROMISE cut points in the PRECISE participant population will be evaluated. Logistic regression model will be used estimate the area under the curve quantified by calculating c-index statistic and mean observed and predicted mean plot. The following lists the outcomes and populations to be evaluated:

- Scenario 1: PRECISE primary endpoint all three components for All Randomized Participants
- Scenario 2: PRECISE primary endpoint two components: Death/MI only for All Randomized Participants
- Scenario 3: Prognostic Value of Risk Score for No CAD + No Event for All Randomized Participants, Only Precision Care Arm Receiving CTA
- Scenario 4: Prognostic Value of Risk Score for Significant or Severe CAD for All Randomized Participants, Only Precision Care Arm Receiving CTA

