The PROMISE Risk Tool was expressly developed to identify low-risk patients with stable chest pain who are unlikely to benefit from non-invasive testing, and for whom guideline-recommended medical management alone may be safe. Current guidelines recommend using a version of the Diamond and Forrester risk score for pretest likelihood of obstructive CAD, but multiple investigators have found that this tool grossly over estimates actual presence of disease^{5, 31, 32}. The consequence is an imprecise evaluation strategy for millions of patients, resulting in unhelpful testing of lower risk individuals. For a significant portion of these, a false positive functional testing leads them to have invasive cardiac catheterizations to rule out the disease they do not have. The Risk Tool developed using the PROMISE cohort employs 10 readily available clinical variables (such as tobacco usage, ethnicity/race, and age) and has been validated in the SCOT-HEART population^{33, 34}. This risk tool identifies patients with stable chest pain who have no coronary plaque or calcification by cCTA and no cardiac events over 2 years, and who therefore would be predicted to derive minimal or no value from noninvasive testing^{33, 34}. Testing whether this risk tool can be employed prospectively to safely and effectively risk stratify low risk patients into a strategy of guideline-recommended care with symptom and risk factor management and without diagnostic testing is one of the core secondary objectives of the PRECISE research program.

III.B. Rationale for the Current Study: A Precision Approach to Chest Pain Evaluation

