6.1 Risk Groups based on PROMISE Risk Score

To calculate the PROMISE risk score use the following table estimates based on the risk score paper (Fordyce, JAMA Cardiology 2017). The Promise Score is equal to $1/(1+\exp(\text{logit}))$.

Logit Equation= $\gamma_1 + \gamma_2 * \text{Age (Years)} + \gamma_3 * \text{Sex(female=1)} + \gamma_4 * \text{Caucasian/Non-Hispanic (no=1)} + \gamma_5 * \text{Tobacco(current or former=1)} + \gamma_6 * \text{Diabetes(yes=1)} + \gamma_7 * \text{Dyslipidemia(yes=1)} + \gamma_8 * \text{Family history of premature (<55 years)Coronary artery disease(yes=1)} + \gamma_9 * \text{hypertension(yes=1)} + \text{Symptoms unrelated to physical or mental stress (not related=1)} + \gamma_{11} * \text{Symptoms unrelated to physical or mental stress(unknown=1)} + \gamma_{12} * \text{HDL (mg/dL)}$

Logit Equation coefficients

		HDL is available	HDL is not available	
			Female	Male
Intercept	γ_1	-3.7524	-3.7524	-3.7524
Age (Years)	γ_2	0.0842	0.0842	0.0842
Sex (female=1)	γ_3	-1.0264	-1.0264	-1.0264
Caucasian/Non-Hispanic (no=1)	γ_4	-0.1422	-0.1422	-0.1422
Tobacco (current or former=1)	γ_5	0.5264	0.5264	0.5264
Diabetes (yes=1)	γ_6	0.3141	0.3141	0.3141
Dyslipidemia (yes=1)	γ_7	0.4122	0.4122	0.4122
Family history of premature (<55 years) Coronary artery disease (yes=1)	γ_8	0.3086	0.3086	0.3086
Hypertension (yes=1)	γ_9	0.4078	0.4078	0.4078

Symptoms unrelated to physical or mental stress (not related=1)	γ_{10}	0.3086	-0.3086	-0.3086
Symptoms unrelated to physical or mental stress (unknown=1)	γ_{11}	-0.195	-0.195	-0.195
HDL (mg/dL)	γ_{12}	-0.00559	-0.318682 HDL constant	-0.252855 HDL constant

Risk groups will be defined as the following:

- Low Risk: Promise Score >0.46
- Elevated Risk: Promise Score ≤ 0.46

Low Risk and Elevated Risk groups are defined using a cut point based on the top 10% of low risk of the PROMISE Risk Score in the PROMISE cohort. Thus, in PRECISE, Low Risk is defined as an absolute score >0.46 .

7. Sample Size and Power Calculations

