Figure 4.12.3.1	Mean observed and predicted mean Prognostic Value of Risk Score for Lowest risk: No CAD + No Event All Randomized Participants, Only Precision Care Arm Receiving CTA
Table 4.12.3.2	Mean observed and predicted mean Prognostic Value of Risk Score for Lowest risk: No CAD + No Event All Randomized Participants, Only Precision Care Arm Receiving CTA
Figure 4.12.4.1	Mean observed and predicted mean Prognostic Value of Risk Score for Significant or Severe CAD All Randomized Participants, Only Precision Care Arm Receiving CTA
Table 4.12.4.2	Mean observed and predicted mean Prognostic Value of Risk Score for Significant or Severe CAD All Randomized Participants, Only Precision Care Arm Receiving CTA
Table 4.13.1	Comparisons of outcomes in low PRMS and elevated risk Adjudicated Endpoint Collection and Summary All Randomized Participants, Low PRMS Only
Figure 4.13.1.1	Kaplan-Meier Plot of Primary Endpoint All Randomized Participants, Low PRMS Only
Figure 4.13.1.2	Kaplan-Meier Plot of Primary Endpoint Component All Cause Death All Randomized Participants, Low PRMS Only
Figure 4.13.1.3	Cumulative incidence Plot of Primary Endpoint Component 1st Non-fatal MI All Randomized Participants, Low PRMS Only
Figure 4.13.1.4	Cumulative incidence Plot of Primary Endpoint Component 1st Invasive cardiac catheterization without obstructive CAD All Randomized Participants, Low PRMS Only
Table 4.13.2	Comparisons of outcomes in low PRMS and elevated risk Adjudicated Endpoint Collection and Summary All Randomized Participants, Elevated PRMS+athero Only
Figure 4.13.2.1	Kaplan-Meier Plot of Primary Endpoint All Randomized Participants, Elevated PRMS+athero Only
Figure 4.13.2.2	Kaplan-Meier Plot of Primary Endpoint Component All Cause Death All Randomized Participants, Elevated PRMS+athero Only
Figure 4.13.2.3	Kaplan-Meier Plot of Primary Endpoint Component 1st Non-fatal MI All Randomized Participants, Elevated PRMS+athero Only
Figure 4.13.2.4	Kaplan-Meier Plot of Primary Endpoint Component 1st Invasive cardiac catheterization without obstructive CAD All Randomized Participants, Elevated PRMS+athero Only
Table 4.15.1	COVID-19 Sensitivity Analysis of Primary Endpoint Endpoint Collection and Summary All Randomized Participants

11. Changes from the Protocol

The current version of the protocol is v1.5, dated 15- OCT-2019. Under section VIII.B., the time to event is defined as the date of the first event minus the date of randomization, and we are adding 1 to this value.

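### SAP 9.3.4.1 does not fix the source of the predictions in its PROMISE score calibration check; if they come from a model fitted in PRECISE, the check cannot show that the published score over- or under-predicts

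*SAP*

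**What the plan says.** SAP 9.3.4.1 sits under Sensitivity Analyses and states its aim as follows: "The calibration and discrimination of PROMISE cut points in the PRECISE participant population will be evaluated". The method is one sentence: "Logistic regression model will be used estimate the area under the curve quantified by calculating c-index statistic and mean observed and predicted mean plot". It covers four outcomes: the three-component primary endpoint (Scenario 1), death or MI (Scenario 2), no CAD and no event in precision-arm CTA recipients (Scenario 3), and significant or severe CAD in the same recipients (Scenario 4).

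The SAP does not give the form of the predictor, whether coefficients are fixed or estimated, the grouping for the plot, a calibration intercept or slope, or a criterion for success. SAP section 10 gives all four scenarios the same output title stem. The Scenario 3 entry, for example, adds only "Prognostic Value of Risk Score for Lowest risk: No CAD + No Event".

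SAP 6.1 makes the score a probability with fixed coefficients ("The Promise Score is equal to" 1/(1+exp(logit))) and sets the cut: "Low Risk: Promise Score >0.46". Protocol III.A says what the tool identifies: patients "who have no coronary plaque or calcification by cCTA and no cardiac events over 2 years". It also names as a core secondary objective: "Testing whether this risk tool can be employed prospectively to safely and effectively risk stratify low risk patients".

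**The concern.** Calibration asks whether the probabilities from an existing score match what happens in new patients. That requires the score's own probabilities as the predictions. If a logistic model is first fitted to the new outcomes, the comparison is between the data and a model tuned to those data, and the published score drops out.

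An analyst could follow the SAP sentence to the letter and produce a plot of good agreement that carries no information on over- or under-prediction by the score. The 0.46 cut is applied as an absolute score and decides who in the precision arm has no planned testing, so its behaviour in PRECISE matters to anyone who wants to use the tool afterwards.

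**Working it through.** The plan gives no figure to reproduce here. The check is partly algebra and partly illustration.

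**1. Which scenarios need a fitted model.** The score is a probability of no plaque and no events.
- Scenarios 1, 2 and 4 have different outcomes, so the score cannot serve as their predicted mean. The planning rates for Scenario 1 are 8% and 5%, pooled (8 + 5)/2 = 6.5%. A mean score of about 0.30 (assumed) is not a prediction of that. A predicted mean on the outcome's scale has to be fitted.
- Scenario 3 is close to the score's own target, so the published probability could be used directly. The text does not say that it will be.

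**2. What fitting forces.** For a logistic model with intercept and predictor x, maximum likelihood solves Σ(y − p̂) = 0 and Σx(y − p̂) = 0.
- The first equation makes the overall observed mean equal the overall predicted mean.
- Regressing y on logit(p̂) only re-expresses the same model, so the intercept is 0 and the slope is 1.
- If x is the binary cut, the second equation makes the observed and predicted means equal in each risk group as well.
- If x is the continuous score, group means may differ, but only through non-linearity.

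**3. What a shift in risk would look like.** Suppose the true odds are half or double those given by the score.
- Score 0.20: odds 0.25. Halved, 0.125/1.125 = 0.111, so observed/expected = 0.56. Doubled, 0.50/1.50 = 0.333, ratio 1.67.
- Score 0.30: odds 0.429. Halved, 0.176, ratio 0.59. Doubled, 0.462, ratio 1.54.
- At the cut of 0.46: odds 0.852. Halved, the true probability is 0.30; doubled, 0.63.

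Averaged over an assumed score distribution (logit normal, mean −1.5, SD 0.7, capped at 0.46; mean score 0.20), observed/expected is 0.57 and 1.61. With mean −0.95, SD 0.75 and no cap (mean score 0.30), it is 0.62 and 1.48. A fitted model gives 1.000 every time. The c-index does not react: with 1050 × 0.8 × 0.9 = 756 CTA recipients under the first distribution it averaged 0.68 whether the odds were right, halved or doubled.

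**4. Simulated data sets, one per row** (840 = 1050 × 0.8 participants; logit score normal, mean −0.95, SD 0.75; fitted model uses logit score). Low-risk means score above 0.46.

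| Assumed truth | Overall: observed / fitted / fixed score | Low-risk group: observed / fitted / fixed score | Intercept, slope of fixed score | c-index of fixed score |
|---|---|---|---|---|
| Odds halved, slope 0.5 | 0.256 / 0.256 / 0.303 | 0.407 / 0.363 / 0.545 | −0.66, 0.47 | 0.595 |
| Uninformative | 0.192 / 0.192 / 0.296 | 0.206 / 0.189 / 0.560 | −1.45, −0.01 | 0.504 |
| Reversed | 0.217 / 0.217 / 0.302 | 0.093 / 0.091 / 0.542 | −2.17, −0.83 | 0.330 |

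The fitted model had intercept 0 and slope 1 in every row. With the binary cut as predictor, both group means matched exactly. In the reversed case the c-index of the fitted model was 0.670, so fitting also hides a score that ranks patients the wrong way round. With a U-shaped relation the fitted model did show a decile gap of up to 0.455.

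**5. Who is in Scenario 3.** In the precision arm about 20% are expected to have no planned testing, and about 30% of those to escalate to CTA: 1050 × 0.20 × 0.30 = 63. Without participants with known atherosclerosis, these 63 are nearly all the CTA recipients scoring above 0.46, about 63/(756 + 63) = 8%. Participants with known atherosclerosis are sent to CTA whatever their score, and most cannot have the no-CAD outcome. If they were 10% to 20% of recipients (assumed) with similar scores, a perfectly calibrated score would still show observed/expected of about 0.90 to 0.80.

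**6. The equation itself.** As printed, SAP 6.1 gives γ10 as +0.3086 when HDL is available and −0.3086 when it is not. The gap is 0.6172 on the logit scale, a factor of exp(0.6172) = 1.85 in the odds.

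**The case against.** The strongest reply is that the SAP never says the model is refitted. That is right. The table mock-ups are in a separate document, and for Scenario 3 the fixed probability could be what is meant. Still, a fixed score needs no regression to give a c-index, three of the four scenarios cannot avoid fitting, and one sentence governs all four. The supportable statement is that the source of the predictions is unspecified and the natural reading is a fitted model.

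A reader might infer that the score cannot fail this check. The documents do not support that. The same sentence plans a c-index, which would be near 0.50 for an uninformative score, and grouped means on a continuous score can expose non-linearity. What is lost is the ability to see over- or under-prediction.

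A reader might also infer that the SAP takes 0.46 to be a 46% chance of minimal risk in PRECISE, or that the cut will be declared valid regardless. SAP 6.1 derives the cut by rank, from the top 10% in the PROMISE cohort, and 9.3.4.1 sets no pass rule, so neither follows.

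Finally, the core secondary objective is addressed more directly by the low-risk stratum comparisons in SAP 9.3.4.2 and 9.5. That stands, and it limits the consequence.

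**Conclusion.** The point holds in a limited form. SAP 9.3.4.1 promises a calibration result but leaves open where the predictions come from. On the natural reading, agreement in the overall mean and a 0/1 intercept and slope are guaranteed. That part is algebra and rests on no assumption beyond fitting with an intercept. The sizes (observed/expected of 0.57 to 0.62 for halved odds and 1.48 to 1.61 for doubled odds, invisible after fitting) rest on assumed score distributions and assumed miscalibration; the documents give neither. Discrimination and non-linearity remain testable. This is a secondary sensitivity analysis of the risk tool and does not touch the primary comparison, the key secondary analysis or allocation, but it should be corrected before the tool's calibration is reported.

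**What to change.** Amend SAP 9.3.4.1 as follows.

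- **Before use:** reconcile the sign of γ10 in the SAP 6.1 table and confirm which equation was implemented.
- **Scenario 3:** take the SAP 6.1 score as the predicted probability, without refitting. Report the observed proportion by score group, the observed/expected ratio, and calibration intercept and slope with 95% CIs. Compute the c-index from the score as published, so that a reversed ranking is visible.
- **Population:** do this in CTA recipients without known atherosclerosis, or report those with it separately. State that follow-up is 12 months against the score's 2-year target, and that few CTA recipients will score above 0.46, so calibration above the cut will be imprecise and will come largely from escalated participants.
- **Scenarios 1, 2 and 4:** report discrimination and observed rates by score group, and drop the calibration claim.

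If fixed predictions were intended for Scenario 3 all along, a sentence settles their source; the γ10, population and other-scenario points remain. The cost is SAP wording and revision of the eight planned outputs 4.12.1.1 to 4.12.4.2, with no new data. The downside is that the check can then give an unfavourable result.

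### Scenario 1 of the PROMISE cut-point validation pools an arm in which the score itself decides who is tested, so part of any discrimination is built in; Scenarios 3 and 4 lack CTA for most participants assigned to no testing

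*SAP*

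**What the plan says.** SAP 9.3.4.1, placed under Sensitivity Analyses, states: "The prognostic cut point used for the PROMISE risk score will be validated in light of the results of PRECISE". The method is "Logistic regression model will be used estimate the area under the curve quantified by calculating c-index statistic and mean observed and predicted mean plot".

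Four analyses follow. The opening pair covers both arms together. One of them is "Scenario 1: PRECISE primary endpoint all three components for All Randomized Participants"; its companion keeps that population but drops the catheterization component, leaving death or MI. The remaining pair rests on CTA findings. The wording for the third is "Prognostic Value of Risk Score for No CAD + No Event for All Randomized Participants, Only Precision Care Arm Receiving CTA", and the fourth applies the same restriction to disease graded as significant or severe.

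The planned outputs 4.12.1 to 4.12.4 in SAP 10 repeat these populations. Neither place plans a version by arm, an adjustment for management, or a correction for who received CTA.

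The cut is set in SAP 6.1 ("Low Risk: Promise Score >0.46"), so a high score means low risk. Under SAP 6, the score and known mild atherosclerosis determine whether a precision participant is assigned to no planned testing or to CTA. Known plaque sends a participant to the elevated stratum, and so to CTA, at any score.

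The final protocol adds three relevant points. Every participant is scored and sites are blinded to the result (IV.G). In the precision arm, invasive angiography is conditioned on at least one of four findings, each of which comes from CTA or FFRCT (IV.G, Subsequent Care). Low-risk participants who later need testing are directed to CTA ahead of elective catheterization, unless the need is urgent (V.E).

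Protocol III.A says that testing prospective use of the tool "is one of the core secondary objectives of the PRECISE research program".

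**The concern.** Validating a prognostic score requires an outcome that the score does not influence through the care it triggers. In Scenario 1 that condition fails in one arm. Catheterization without obstructive CAD is a care process, and in the precision arm it ordinarily follows a CTA. A participant assigned to no testing is largely kept from that component by the assignment, whether or not the score says anything about disease. Pooling the arms carries this into the c-index and into the observed-rate plot.

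Scenarios 3 and 4 have a different problem. The tool was built to identify people with no plaque and no events (Protocol III.A), which is the Scenario 3 outcome. CAD status is known only after a CTA, and most participants assigned to no testing will not have one.

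What is at stake is a statement that the 0.46 cut was validated, resting partly on the assignment rule and partly on a set with few low-risk participants. The treatment comparison is not at stake.

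**Working it through.** SAP 9.3.4.1 gives no c-index, sample size or precision, so there is no stated figure to reproduce. The check asks what a score with no prognostic value would show.

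**Inputs from SAP 7:** 1050 per arm; 8% (usual care) and 5% (precision) event rates at one year; about 20% of the precision arm assigned to no testing, of whom about 30% escalate to CTA; 10% not receiving their randomized evaluation. For Scenario 1 that 10% is already inside the 8% and 5% and is not modelled again. Expected events use 12-month rates, because SAP 9.2 stops at 395 days; the 202 in SAP Table 1 is close to what 12 to 24 months of follow-up would give.

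**Assumed, not in the documents:** a 1% event rate in untested participants (range 0.5% to 2%), the same in both risk groups.

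**Scenario 1**

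- Untested share of the precision arm: 0.20 × 0.70 = 0.14. Tested share: 0.86.
- Tested rate x solves 0.14 × 1% + 0.86x = 5%, so x = 5.65%.
- Low-risk rate: 0.70 × 1% + 0.30 × 5.65% = 2.40%. Elevated rate: 5.65%.
- For an uninformative score, c = 0.5 + 0.5 × [P(low | no event) − P(low | event)].
- Precision arm: P(low | no event) = 0.2 × 0.9760 / 0.95 = 0.2055; P(low | event) = 0.2 × 0.0240 / 0.05 = 0.0958; c = 0.555.
- Usual care: 8% in both groups, so c = 0.500.
- Pooled rates: low (8 + 2.40)/2 = 5.20%; elevated (8 + 5.65)/2 = 6.83%. That is about 24% fewer events in the low group. Then 0.2 × 0.9480 / 0.935 = 0.2028 and 0.2 × 0.0520 / 0.065 = 0.1599, so c = 0.521.

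| Event rate if untested | c, precision arm | c, pooled |
|---|---|---|
| 0.5% | 0.562 | 0.524 |
| 1% | 0.555 | 0.521 |
| 2% | 0.541 | 0.516 |

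Varying the low-risk share from 10% to 30% and escalation from 10% to 50% gives a pooled c of 0.506 to 0.548. The 20% is the share assigned to no testing, not the share above 0.46. Known-plaque participants above the cut are tested, so including them in the low-score group would dilute the effect somewhat.

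Expected events: 2100 × 6.5% = 136.5 pooled; 1050 × 8% = 84 in usual care. The null standard error of c for a continuous score is about 0.026 pooled and 0.033 in usual care (Hanley-McNeil). For the two-level cut it is 0.5 × √[0.2 × 0.8 × (1/136.5 + 1/1963.5)] = 0.018 pooled.

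**Scenario 2**

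If testing does not alter death or MI, c = 0.500. Suppose instead that CTA carries the 12-month hazard ratio of 0.66 that Protocol III.A reports from PROMISE, and that untested participants have the usual-care rate r. Precision low risk is then 0.70r + 0.30 × 0.66r = 0.898r, against 0.66r for elevated. Pooled, this is 0.949r against 0.83r, and c = 0.489. Any bias runs against the score.

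**Scenarios 3 and 4**

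- Assigned to no testing: 1050 × 0.20 = 210. No CTA: 210 × 0.70 = 147. Escalated to CTA: 63.
- CTA set: 63 + 840 × 0.90 = 819. Low risk is 63/819 = 7.7% of it, against 20% of the arm.
- Uninformative score, Scenario 3, with 27% free of plaque (the PROMISE share in Protocol III.B): c = 0.500 if escalation is unrelated to CAD, and 0.491 to 0.468 if the escalated group has 22% down to 10% free of CAD (assumed).
- Informative score, simulated with an assumed true c of 0.70: c in the CTA set is 0.675, or 0.651 if those with CAD are 1.8 times as likely to escalate. The two-level cut falls from 0.613 to 0.555 when escalation is unrelated to CAD.
- With 63 escalated participants, a 27% proportion has a 95% half-width of 1.96 × √(0.27 × 0.73 / 63) = 11 percentage points.

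**The case against.** A reader might infer that all four scenarios would make a worthless score look useful. The documents do not support that. Death and MI are not directed by the score, and CAD seen on CTA is not produced by it; the score affects only who is imaged. For Scenarios 2, 3 and 4 the calculation gives no inflation.

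The Scenario 1 artefact is also modest. The pooled excess of about 0.021 is below one standard error of a continuous-score c (0.026), and 0.555 belongs to a precision-arm analysis that the SAP does not list. This stands as to size. It is still a bias: more events would not remove it. Against the two-level cut's standard error of 0.018 it is about 1.2 standard errors, and the observed-rate plot would show it as well.

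The core objective is better served by the randomized comparisons within risk strata (SAP 9.3.4.2 and 9.5), and SAP 10 already splits the usual-care columns by risk. That is true of the safety of the strategy. Those comparisons estimate strategy effects, however, and leave the c-index and calibration plot as they are.

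The CTA restriction is openly stated and largely forced. CTA is excluded as the first test in usual care and prohibited for 45 days (SAP 6), so no better population exists for Scenarios 3 and 4. This stands, and it is why their remedy is description rather than a different analysis set.

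Usual care alone would have only about 1050 × 1% to 2% = 10.5 to 21 death or MI events, at the annual rates in Protocol III.A. This stands too, and is a reason to keep the pooled Scenario 2 result.

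**Conclusion.** The point holds for Scenario 1. Pooling the arms builds in discrimination of about 0.02 in c (0.516 to 0.524 instead of 0.500) and a low-versus-elevated contrast of about 5.2% against 6.8%. In the precision arm alone c would be about 0.555. These sizes rest on the SAP's planning figures and on an assumed 0.5% to 2% event rate in untested participants.

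Scenarios 3 and 4 are limited by partial verification. About 147 of 210 participants assigned to no testing have no CTA, and the remaining 63 or so are selected mainly by persistent symptoms. This tends to understate the score.

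A reader might also conclude that PRECISE cannot validate the cut at all. That goes too far: every participant is scored, sites are blinded, and the score does not direct care in usual care, where an uninformative score gives c = 0.500. The section is a sensitivity analysis and the primary test is unaffected, but its wording promises validation of a tool whose prospective use the protocol counts among its core secondary objectives.

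**What to change.** In SAP 9.3.4.1 and outputs 4.12.1 to 4.12.4:

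- Report Scenarios 1 and 2 by arm. Name usual care as the validation set for Scenario 1 and show the precision arm separately. Clinicians in usual care still see the variables behind the score, so the estimate describes prediction under usual practice.
- Keep the pooled Scenario 2 result alongside the by-arm results, because usual care alone has few death or MI events.
- Describe Scenarios 3 and 4 as performance among CTA-tested precision-arm participants, not as validation of the 0.46 cut. Give separate denominators for score ≤0.46, escalated low-risk participants, and known-plaque participants with score >0.46.

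The cost is SAP wording and a few extra table columns, plus precision for Scenario 1: 84 of 136.5 expected events remain (62%), and the null standard error of c rises from about 0.026 to 0.033. No new data are needed.
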